## **13) Statistical Analysis Plan:**

fNIRS data analysis will follow the standard processing steps. This includes spatial registration (recording of standard cranial landmarks nasion, inion, left and right ear, and the 3D locations of the fNIRS probes); transformation to MNI space [39]; band-pass

filtering for motion artifact removal; and estimation of the hemodynamic response function using GLM, as implemented in the NIRS Toolbox for MATLAB. Comparisons between baseline and task HbO will reveal task-related de/activations, corrected for multiple comparisons (52 channels). Average HbO changes will then be determined for each channel and each measurement and entered into second-level analysis. Similarly, means of HbO for pre and post-stimulation will be entered into second-level analysis.

A t-test between pre- and post-stimulation in condition 1 will be performed to test hypothesis 1. Hypothesis 1 will be supported if there is a significant increase in prefrontal HbO after stimulation.

A t-test between condition 2 and 1 using change scores will be performed to test hypothesis 2. Hypothesis 2 will be supported if there is a significant stronger change in HbO in condition 1 compared to condition 2

A t-test between condition 3 and 1 using change scores will be performed to test hypothesis 3. Hypothesis 3 will be supported if there is a significant stronger change in HbO in condition 3 compared to condition 1.

A t-test between pre- and post-stimulation in condition 4 and between change scores of condition 1 and 4 will be performed to test hypothesis 4. Hypothesis 4 will be supported if there is a significant increase in prefrontal HbO after stimulation, but no significant difference in change scores between condition 1 and 4.

Regarding the three exploratory hypotheses about participants' behavior (reaction times, hits and misses) and HbO changes during cognitive tasks, linear mixed models will be conducted to determine differences between conditions, followed by post-hoc pairwise comparisons. Here, a three-way interaction between time, condition and emotion will be evaluated and followed by post-hoc two-way interactions and pairwise comparisons.

Hypothesis E1 will be supported if there is a significant change in HbO and/or behavioral measures in condition 1 in some (e.g. sad) but not other emotions (e.g. happy) after stimulation (following a post-hoc 2-way interaction between time and emotion).

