Hypothesis E2 will be supported if there is a significant interaction between time, emotion and conditions 2 and 1.

Hypothesis E3 will be supported if there is a significant interaction between time, emotion and conditions 3 and 1.

Hypothesis E4 will be supported if there is a significant change in condition 4 in some (e.g. sad) but not other emotions (e.g. happy) after stimulation (following a post-hoc 2-way interaction between time and emotion).

Finally, two t-tests comparing ERA- recognition accuracies between subclinically depressed and control participants and between pre and post stimulation in the sample of subclinically depressed participants will be performed in order to test hypotheses E5 and E6, respectively.

Hypothesis E5 will be supported if recognition accuracy is reduced in participants with subclinical depression compared to the control sample.

Hypothesis E6 will be supported if recognition accuracy will be increased after stimulation compared to baseline in participants with subclinical depression.

Behavioral data will be analyzed using the IBM SPSS software (<http://www-01.ibm.com/software/analytics/spss/>). The alpha level will be set at 0.05, adjusted for multiple comparisons using the Bonferroni-Holm procedure. For GLM, post-hoc pairwise comparisons will be corrected using Fisher least significant difference procedure in accordance with the closed test principle, i.e., post hoc comparisons will be declared nonsignificant if the global p value of the main- or interaction effect is nonsignificant, but carried out without further correction in case of a significant global effect.

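### Fisher LSD after one global test is not a closed test with four conditions, so familywise error for the exploratory condition pairs is not held at 5%

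*Combined protocol and SAP*

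**What the plan says.** Section 13 (Statistical Analysis Plan) gives two multiplicity rules.

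- A general rule: "The alpha level will be set at 0.05, adjusted for multiple comparisons using the Bonferroni-Holm procedure".
- A rule introduced for GLM: "post-hoc pairwise comparisons will be corrected using Fisher least significant difference procedure in accordance with the closed test principle". The SAP explains it in two halves. First, "post hoc comparisons will be declared nonsignificant if the global p value of the main- or interaction effect is nonsignificant". Second, once the gate is passed, pairs are "carried out without further correction in case of a significant global effect".

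Section 10 (Interventions) lists four arms and 80 participants, with no allocation ratio.

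Condition pairs arise in the exploratory analyses of task HbO and behaviour, where "linear mixed models will be conducted to determine differences between conditions, followed by post-hoc pairwise comparisons". Section 13 adds that a three-way interaction of time, condition and emotion is evaluated there, followed by two-way interactions and pairs. The term GLM appears in only one other place, the first-level signal processing: "estimation of the hemodynamic response function using GLM".

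**The concern.** A closed test rejects a pair only if every intersection hypothesis that includes the pair is also rejected at 0.05. This gives strong control: the chance of any false pair stays at or below 5% whichever conditions truly differ. The SAP claims that property for a procedure which, with four conditions, does not have it.

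The gate protects only when all four conditions are equal. Once one condition truly differs, that difference can open the gate, and the remaining equal conditions are then compared with one another at an unadjusted 0.05. A reader who trusts the closed-test label would take a significant condition pair for task HbO or reaction time as familywise-controlled at 5%.

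**Working it through.** **1. Count the hypotheses.** Four condition means give 14 hypotheses of equality: 1 global + 4 with three conditions equal + 3 with two separate pairs equal + 6 single pairs. The SAP tests 1 + 6 = 7 and omits 4 + 3 = 7. Each pair lies inside the global hypothesis, two three-condition hypotheses and one two-pair hypothesis. With three groups, any two pairs together imply the global hypothesis, so nothing is omitted and LSD is closed. Simulated error for three groups is 4.9–5.0%.

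**2. Inputs.**
- From the documents: 4 arms, 80 participants, alpha 0.05.
- Assumed: 80/4 = 20 per arm, two-sided tests, pooled variance on 80 − 4 = 76 df, effects in SD units.

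The SAP gives no error rate for the procedure beyond the 5% that the closed-test label implies.

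**3. Ceiling.** Suppose one condition is far from the rest. The gate then always opens, and three equal means are compared without adjustment.
- Unadjusted cut-off: t(0.975, 76 df) = 1.992.
- On the studentized-range scale: 1.992 × √2 = 2.817.
- P(studentized range of 3 means, 76 df > 2.817) = 12.1%, which is 12.1/5 = 2.4 times nominal.

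With two separate equal pairs the approximate ceiling is 1 − 0.95² = 9.75% (simulated 9.7%).

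**4. One-way condition gate.** Simulation with 200,000 trials per case: global F at 0.05, then six unadjusted t-tests. An error is any rejection among truly equal pairs.

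| True pattern | Gate passes | LSD error | Full closed error |
|---|---|---|---|
| All four equal | 5.0% | 5.0% | 4.9% |
| One differs, 0.3 SD | 13.6% | 5.9% | 3.7% |
| One differs, 0.5 SD | 32.3% | 8.7% | 4.4% |
| One differs, 0.8 SD | 71.6% | 11.5% | 5.0% |
| One differs, 1.0 SD | 90.3% | 11.8% | 4.9% |
| One differs, 3 SD | 100% | 12.2% | 5.1% |
| Two and two, 0.5 SD | 42.0% | 8.0% | 3.9% |
| Two and two, 0.8 SD | 84.7% | 9.6% | 4.6% |
| Condition 2 lower, 3 higher, 1 = 4, 0.5 SD | 73.6% | 4.7% | 3.3% |
| Same pattern, 0.8 SD | 99.2% | 5.1% | 4.8% |

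Separate runs gave 8.5–8.7% at 0.5 SD and 11.3–11.5% at 0.8 SD. With 16 analysed per arm (an assumed dropout), one condition differing gives 7.9% at 0.5 SD and 10.8% at 0.8 SD.

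**5. Three-way interaction gate.** Change scores, 20 per arm, condition 3 differing in one emotion, six pairs within that emotion. The documents give neither the number of emotions nor the within-person correlation, so these were varied: 2–6 emotions, correlation 0–0.7, no intermediate gate.

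| Difference in the one emotion | LSD error |
|---|---|
| 0.5 SD | about 3–7% (below 5% for correlation 0.5 or less) |
| 0.8 SD | about 6–12% |
| 1.0 SD | about 9–12% |

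This gate opens less often for a moderate effect confined to one emotion, so the inflation starts later. The ceiling of about 12% is the same.

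**The case against.** **The rule may not cover these models.** The SAP calls the exploratory models linear mixed models and uses GLM elsewhere only for the haemodynamic response. If the rule does not reach the mixed models, the Bonferroni-Holm sentence applies and there is no inflation. This stands as a condition on the point. Coverage is still the natural reading: the rule speaks of main and interaction effects, interactions appear only in the mixed models, and haemodynamic response estimation has no condition pairs.

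**The size depends on the gate and the pattern.** This also stands. A reader might infer an error of 9–12% whenever a condition differs by 0.5 SD or more. The documents do not support that. It is roughly right for a one-way gate with 20 per arm, but not with 16 per arm, and not for the three-way gate that section 13 describes. Under the pattern that section 9 hypothesises for resting HbO, only one pair is truly equal and error is about nominal. Strong control, however, must hold for every pattern, and section 9 states no such four-condition pattern for the task outcomes.

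**The SAP discloses that pairs are uncorrected, and the hypotheses are exploratory.** Both are true, but neither cures the problem, because the same sentence calls the rule closed.

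**No named hypothesis rests on the full six-pair family.** Largely correct. A reader might infer that the primary outcome is compromised, but H1–H4, E5 and E6 are t-tests outside this rule. E2 and E3 are interactions limited to one pair of conditions each (for example, "Hypothesis E2 will be supported if there is a significant interaction between time, emotion and conditions 2 and 1"). If those two pairs were taken as post-hoc pairs under LSD, the one-way error over them would be at most 5.0% when condition 2 or 3 differs. It would be 6.7% (0.5 SD) to 9.0% (3 SD) when condition 4 differs. E1 and E4 concern change within one condition by emotion ("Hypothesis E4 will be supported if there is a significant change in condition 4 in some"). Error control across emotions is a different question and is not assessed here.

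**Conclusion.** The closed-test statement is wrong as written for four conditions, whatever the effect sizes. The consequence for error rates is conditional on the rule covering the linear mixed models. If it does, familywise error over six condition pairs is not held at 5% and can reach about 12% when one condition differs strongly. How early it rises depends on the gate, the number per arm and the correlation between emotions, none of which the documents fix. The effect is confined to post-hoc condition pairs for the secondary and exploratory task HbO and behavioural outcomes. Severity is minor. Confidence is moderate, because the scope of the GLM rule is not stated.

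**What to change.** State that the rule covers the linear mixed models, and name the global test that serves as the gate. Then make the procedure closed within each six-pair family: declare a pair only if the global test, the two three-condition tests containing it, the two-pair test containing it and the pair itself are all significant at 0.05. The global test should be the four-condition test for that family. If the SAP gates on the three-way interaction, the four-condition test within the emotion has to be run as well.

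The cost is seven extra contrasts per family (eight in that last case) in a model already fitted, with no new data. In the one-way case with one condition differing, the chance of declaring a true pair falls from 23% to 18% at 0.5 SD, from 62% to 53% at 0.8 SD, and from 84% to 77% at 1.0 SD. Bonferroni-Holm over the six pairs also controls the error but costs more power (15%, 46% and 71%).

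If the sponsor prefers plain LSD, delete the reference to the closed test principle and report these pairs without a claim of familywise control. That is a wording change only.

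### On the natural reading of section 13, E1 and E4 can be declared only if the time × condition × emotion interaction is significant, a test whose null does not imply theirs

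*Combined protocol and SAP*

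**What the plan says.** All of this is in section 13, Statistical Analysis Plan, of the combined protocol and SAP.

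- **Model.** For the exploratory hypotheses, "linear mixed models will be conducted to determine differences between conditions, followed by post-hoc pairwise comparisons".
- **Order of testing.** In these models, "a three-way interaction between time, condition and emotion will be evaluated and followed by post-hoc two-way interactions and pairwise comparisons".
- **E1** requires a "significant change in HbO and/or behavioral measures in condition 1 in some (e.g. sad) but not other emotions (e.g. happy) after stimulation". The plan places this after a time × emotion interaction that it labels post hoc.
- **E4.** "Hypothesis E4 will be supported if there is a significant change in condition 4 in some (e.g. sad) but not other emotions", again after a post-hoc time × emotion interaction.
- **Gate.** "For GLM, post-hoc pairwise comparisons will be corrected using Fisher least significant difference procedure in accordance with the closed test principle"; the same sentence explains that "post hoc comparisons will be declared nonsignificant if the global p value of the main- or interaction effect is nonsignificant". The other half of the rule, for a global test that succeeds, reads: "but carried out without further correction in case of a significant global effect".
- **Alpha.** "The alpha level will be set at 0.05, adjusted for multiple comparisons using the Bonferroni-Holm procedure".

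No other route to E1 or E4 is described. Section 10 gives iTBS to all four arms, including the control arm, where it follows sham priming.

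**The concern.** E1 and E4 each ask a question about one condition: did responses to some emotions change from before to after stimulation while others did not? The three-way interaction asks something else, namely whether that emotion pattern differs between conditions. If all four arms show the same emotion-specific change, E1 and E4 are true and the three-way null is also true. A gate on the three-way test then blocks both, however large the change is.

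The plan appeals to the closed test principle. That principle permits gating a hypothesis on a global null when the global null is an intersection that includes the individual null, so that the first being true makes the second true. Here it does not: an equal pattern across arms is compatible with a strong pattern in every arm.

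At stake is the ability to declare two exploratory findings in support of the second objective in section 9 (facial emotion processing and executive function). The resting-HbO analogues, hypotheses 1 and 4, use pre-post t-tests within the condition and need no significant interaction first.

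**Working it through.** **Inputs.** Alpha 0.05, the gate and the order of testing come from section 13. The 80 participants and four arms come from section 10. The plan gives no allocation ratio, effect size, SD, power or number of emotions, so there is no power figure to reproduce. Assumed: 20 per arm; k = 2, 3 or 6 emotions; one emotion shifted by d residual SDs of the change score.

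**Step 1: the bound when priming does nothing.** All arms then share one time × emotion profile and the three-way null is true.

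P(E1 declared) = P(gate opens and E1 test significant) ≤ P(gate opens) = 0.05.

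The same holds for E4. Each is declared nonsignificant at least 95% of the time per outcome model. This needs no effect size and no sample size.

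**Step 2: several outcomes.** E1 may be met on HbO or on behavioural measures. With m independent outcomes, each gated at an unadjusted 0.05, P(at least one gate opens) = 1 − 0.95^m:

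- m = 2: 9.8%
- m = 3: 14.3%
- m = 4: 18.5%, so all four gates stay shut in 0.95⁴ = 81% of trials

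If Bonferroni-Holm spans the outcomes, the chance that any gate opens returns to 5% or less.

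**Step 3: simulation with no priming effect.** The three-way test is the condition × emotion F test on change scores; the E1 test is the emotion F test within condition 1. There were 8,000 runs per setting. Ranges are over k.

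| d | Gate opens | E1 test, ungated | E1 test behind gate |
|---|---|---|---|
| 0.5 | 0.043–0.050 | 0.28–0.33 | 0.021–0.025 |
| 0.8 | 0.048–0.053 | 0.67–0.71 | 0.032–0.038 |
| 1.2 | 0.051–0.053 | 0.95–0.97 | 0.045–0.050 |
| 2.0 | 0.049–0.052 | 1.00 | 0.049–0.052 |

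The gate opens at its nominal 5%, within Monte Carlo error of about 0.25 points. Gated E4 ranges from 0.020 to 0.052.

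**Step 4: priming as hypothesised.** Section 9 expects 0 minutes to eliminate the iTBS effect, 10 minutes to potentiate it and 20 minutes to match sham priming, and states this for resting fNIRS. Carrying that pattern over to the tasks, with assumed multipliers 1, 0, 1.5, 1 for arms 1 to 4 (5,000 runs per setting):

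| d | Gate opens | E1 test, ungated | E1 test behind gate |
|---|---|---|---|
| 0.5 | 0.21–0.27 | 0.29–0.33 | 0.10–0.11 |
| 0.8 | 0.58–0.62 | 0.68–0.72 | 0.42–0.46 |
| 1.2 | 0.94–0.96 | 0.95–0.98 | 0.90–0.93 |

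In both tables the power is for the condition 1 time × emotion test. E1 as defined also needs change in some emotions and not in others, so these are not full power figures for E1.

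**Step 5: error control once the gate is open.** Suppose only condition 3 has an emotion-specific change and the gate is open. E1 and E4 are then each tested at an uncorrected 0.05 while both nulls are true. If the tests are independent, the familywise error is 1 − 0.95² = 9.8% per outcome. The gate does not protect this pair.

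**The case against.** **The gate may not apply to E1 and E4.** The rule is worded for GLM and for pairwise comparisons, while E1–E4 use linear mixed models, and a two-way interaction is not a pairwise comparison. It also refers to a main or interaction effect without naming one. It could be read as gating the per-emotion comparisons on the two-way interaction they follow; the 95% figure would then fall away. This reading is possible, so the gate is an inference and not an explicit statement. But section 13 makes the two-way interactions themselves follow the three-way test, and the exploratory mixed models are the only second-level analyses it describes with interactions and post-hoc comparisons. The three-way gate remains the natural reading, and the ambiguity itself needs resolving.

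**The 95% is not a trial-level figure.** A reader might infer that E1 fails in 95% of trials in which priming is inert. That holds per outcome model, or overall if Bonferroni-Holm spans the outcomes. The plan does not say that it does. With unadjusted gates the bound is looser, as step 2 shows. The extra openings are chance rejections of a true three-way null.

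**The loss depends on priming being inert.** This stands. Under the hypothesised pattern the loss is material at 0.8 SD and small at 1.2 SD.

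**These hypotheses are exploratory.** This also stands, and it limits the consequence. It does not make the gate logically valid.

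**Conclusion.** The point holds on the natural reading of section 13. E1 and E4 sit behind a test that can be correctly nonsignificant while both are true, and the closed test principle does not support that arrangement. With inert priming, a real emotion-specific change common to all arms is declared nonsignificant at least 95% of the time per outcome model; this rests on alpha alone. The power losses under active priming rest on the assumed 20 per arm, the effect sizes and the multipliers.

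Three stronger inferences are not supported:

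- **That the primary analysis is affected.** Resting-HbO hypotheses 1–4 are t-tests outside this gate.
- **That every priming question depends on E1.** E2 and E3 compare conditions directly and do not need E1 to be significant.
- **That the plan would report a blocked E1 as absence of an iTBS effect, or that an ungated E1 would establish one.** The SAP does not say how a nonsignificant result will be reported. Because every arm receives iTBS, a pre-post change in condition 1 cannot by itself be separated from retest effects.

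**What to change.** Amend section 13 as follows:

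1. Make the time × emotion tests within condition 1 (E1) and within condition 4 (E4) planned contrasts from the same mixed model, tested whatever the three-way result.
2. Apply the plan's Bonferroni-Holm procedure across both contrasts and all outcomes that can support them. Holm over the two contrasts alone would leave the and/or choice of outcomes in E1 uncontrolled.
3. Gate the per-emotion comparisons within a condition on that condition's own time × emotion test.
4. Keep the three-way gate for E2 and E3 only, where differences between conditions are the question.
5. State which global effect gates which hypothesis, and that the rule applies to the mixed models.

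**Cost.** This is a change of SAP wording; it needs no new data or participants. The price is a stricter threshold. With two contrasts on two outcomes, the first Holm step is 0.05/4 = 0.0125. For the condition 1 test, the noncentral F with λ = 20·d²·(1 − 1/k) and degrees of freedom k − 1 and 19(k − 1) (for k = 2 and d = 0.8, λ = 20 × 0.64 × 0.5 = 6.4) gives power at that step of 0.43–0.49 at 0.8 SD and 0.84–0.92 at 1.2 SD for k = 2, 3 and 6. Later Holm steps, and an error term pooled over arms, raise this. If priming acts as hypothesised, power is therefore roughly what the gated plan gives, or slightly lower at 1.2 SD. The gain is proper error control for the pair, and the removal of the 0.05 ceiling when priming does nothing.
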